#### **Study Role:**

Name

Research Support Staff

View: CRU DSMP Data Collection Simple View Name: Chart Review, interview, questionnaire Level of Risk: Minimal and Low Risk Studies

Type: Data Collection

View: CRU DSMP Data Collection Simple View

Name: Elderly Population

Level of Risk: Moderate Risk Studies

Type: Study Population

View: CRU DSMP Data Collection Simple View

Name: Psychologically or neurologically impaired population

Level of Risk: Moderate Risk Studies

Type: Study Population

View: Create CRU Procedure Risk

C	CRU Procedure Risk:		
	Procedure		Risk

	* Outcomes Assessments (questionnaires, tests of arm and shoulder movement, pain thresholds)  v: Create CRU Procedure Risk  CRU Procedure Risk:	* Name  Minimal or Low  Moderate  High
Ш	Procedure	Risk
	* Percutaneous electrode implant procedure/short term implant and e-stim	* Name  Minimal or Low  Moderate  High
Viev	v: Create CRU Procedure Risk	
 	CRU Procedure Risk:	
Ш	Procedure	Risk
	* Percutaneous electrode removal	* Name  Minimal or Low  Moderate  High
	w: Create CRU Procedure Risk	
Ц'	CRU Procedure Risk:	
Щ	Procedure	Risk
	* Physical Therapy	* Name  Minimal or Low  Moderate  High
	w: Create CRU Procedure Risk	
	CRU Procedure Risk:	
$\square$	Procedure	Risk
	* Venipuncture	* Name Minimal or Low Moderate

				Name High
Vie	View: Create CRU Procedure Risk			
	C	RU Procedure Risk:		
		Procedure		Risk
		* X-Ray		* Name  Minimal or Low  Moderate  High

Clinical Trials Cover Page: Study Protocol and Statistical Analysis Plan

Document Date: 11/5/2021

Multimodal Treatment for Hemiplegic Shoulder Pain

NCT02893267

Expectations and Analysis Compare the efficacy of PNS vs. PT in reducing HSP.

Hypothesis 1. The reduction in HSP will be greater in PNS alone vs. PT alone. Based on Preliminary Studies 1 and 2, an average reduction of 5 points (63%, assuming baseline of 8) in BPI SF-3 is anticipated for the PNS+shamPT group by EOT with maintenance of this effect at follow-up (Figure 7). Based on Preliminary Study 2, a 34% reduction is anticipated by the end of treatment for PT+shamPNS group, increasing to a 20% decrease by the end of follow-up. We anticipate an 87.5% reduction, or 2-points more than PT +shamPNS, by end of treatment for the PNS+PT group, maintaining this level at the end of follow up. The anticipated difference of at least 2.0 points between groups at 28-wks is the minimum clinically important difference in pain scores.152 153 In order to detect this difference with 80% power, α =0.05 (combined), and anticipated SD of 2.4, the minimum sample size is 27/group is necessary when using a one-sided, two-sample, equal-variance t-test of 3 pairwise comparisons (assuming pain reduction with PNS + PT >

[figure not shown]

Figure 7: Anticipated average BPI SF-3 trajectories for participants assigned to PNS+PT (dashed, diamond) PNS+shamPT(solid, triangle), and PT+shamPNS (dotted, square). Shaded area indicates treatment.

PNS+shamPT > PT + shamPNS). With the anticipated drop-out rate of 20%, this leads to a sample size of 32/group for a total of 96 participants.

Exploratory looks at the data across the three groups are done first before fitting our models. Poolability of data across sites will be evaluated and adjusted for as needed. Comparability of demographics by site will be assessed. Treatment by site interaction will be tested. Each measure will be modeled using a linear mixed effects approach which is well-suited for handling correlated repeated measurements, unbalanced data, missing data and dropouts in longitudinal studies. These mixed effects models yield estimates of the treatment, time and treatment by time while permitting us to control for potential confounders. Analysis for comparison of responders will be completed with logistic regression analysis with treatment group as independent variable.

AIM 2. Compare the efficacy of PNS + PT, PNS + ShamPT, and PT + ShamPNS in reducing HSP.

Hypothesis 2. The reduction in HSP will be the greatest with PNS + PT, followed by PNS + Sham PT, and finally PT + Sham PNS. Continuous data will be analyzed using the approach described for hypotheses 1. As a phase II trial, power analysis was conducted only for the primary outcome measure (Worst Pain in the Last Week, BPI SF-3).

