This is your abstract also known as a synopsis from an industry sponsored study. Please limit to 500 words.

experienced an average pain reduction of 33% by the end of treatment. Combining PNS and PT, which may be how PNS is actually implemented in clinical practice, may have a synergistic therapeutic effect. Thus, the second objective of this multisite RCT is to determine if multimodal treatment of HSP with PNS + PT is more efficacious for pain relief than PNS alone or PT alone.

The mechanisms behind PNS and PT for the treatment of HSP are not known. The onset of HSP is associated with the severity of hemiparesis and the resultant biomechanical impairment of the shoulder. [12, 26-28] Our team and others have found that in the chronic stage central mechanisms may also have a role in perpetuating pain, [10, 29-32] as it does in other forms of chronic shoulder pain. [9] Thus, our third objective is to explore mechanisms of PNS and PT for the treatment of HSP. PNS and PT may reduce chronic HSP via central mechanisms, or by improving shoulder biomechanics, or both. These mechanisms will be explored via measures of sensory and pain perception (mechanical pain thresholds, secondary hyperalgesia, and temporal summation) and clinical measures of impairment (shoulder abduction torque, shoulder kinematics, Fugl-Meyer score.)

This pilot-phase II device trial will advance the knowledge about chronic HSP treatment by testing single and multimodal treatments to produce greater pain reduction and increase the number of responders. Information regarding mechanism of action that may lead to future treatment improvements will also be generated. The collaborators involved in this project are leaders in utilizing PNS to reduce pain and disability after stroke and are well positioned to carry out this trial.

7.2 \* What are the specific aims of this study i.e. what are the question(s) this research intends to answer? Provide at a maximum 3 primary and 3 secondary aims.

AIM 1. Compare the efficacy of PNS vs. PT in reducing HSP. Hypothesis 1. The reduction in HSP and associated improvements in upper limb related ADLs and QoL will be greater with PNS alone versus PT alone.

AIM 2. Compare the efficacy of PNS + PT, PNS + ShamPT, and PT + ShamPNS in reducing HSP.

Hypothesis 2. The reduction in HSP and associated improvements in upper limb ADLs, and QoL will be the greatest with PNS + PT, followed by PNS + Sham PT, and finally PT + Sham PNS.

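### Does naming PT+shamPNS as the comparator for the 2-point gain of PNS+PT undermine the sample size?

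*SAP*

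**What the plan says.** The SAP (Expectations and Analysis, under Hypothesis 1) gives an expected course on BPI SF-3, the worst-pain item, for each arm:

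- **PNS+shamPT:** "an average reduction of 5 points (63%, assuming baseline of 8) in BPI SF-3 is anticipated for the PNS+shamPT group by EOT". The SAP expects the gain to persist after treatment ends.
- **PT+shamPNS:** "a 34% reduction is anticipated by the end of treatment for PT+shamPNS group, increasing to a 20% decrease by the end of follow-up".
- **PNS+PT:** "We anticipate an 87.5% reduction, or 2-points more than PT +shamPNS, by end of treatment for the PNS+PT group", with that level held to the end of follow-up.

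It then sets the effect used for sizing: "The anticipated difference of at least 2.0 points between groups at 28-wks is the minimum clinically important difference in pain scores". With 80% power, a combined alpha of 0.05 and an SD of 2.4, it concludes that "the minimum sample size is 27/group is necessary when using a one-sided, two-sample, equal-variance t-test of 3 pairwise comparisons". The same sentence assumes that pain reduction is largest with PNS+PT, then PNS+shamPT, then PT+shamPNS. Drop-out of 20% takes the plan to 32 per group and 96 in total.

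The Protocol abstract (7.1) makes PNS versus PT the primary objective. The combination is the second objective, on the ground that it "may have a synergistic therapeutic effect".

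**The concern.** The sentence about PNS+PT contradicts the figures around it. It attaches a 2-point gap to a pair whose expected gap is more than twice that, and 2.0 points is also the number from which the sample size is derived.

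The text sits under Hypothesis 1, which compares PNS with PT. A reader could therefore take the 80% power to describe a comparison against PT. On the planned means, the pair separated by exactly 2.0 points is PNS+PT versus PNS+shamPT, which is the Aim 2 question of what PT adds to PNS. If the sample size really rested on the pair named, either the effect or the 27 per group would be wrong. A null result could also be misread, because the three contrasts do not have equal power.

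**Working it through.** **Inputs (SAP, Expectations and Analysis).** Baseline 8; PNS+shamPT 5 points, maintained; PT+shamPNS 34% at end of treatment and 20% at end of follow-up; PNS+PT 87.5%, maintained; SD 2.4; combined alpha 0.05 over 3 one-sided pairwise t-tests; power 80%. The baseline of 8 is written in the PNS+shamPT clause. Randomisation makes it reasonable to use it for all arms.

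**1. Reproduce the 27 per group.** Alpha per comparison is 0.05/3 = 0.01667, one-sided. Power comes from a noncentral t with 2n − 2 degrees of freedom and noncentrality δ / (σ√(2/n)). At n = 27 this is 2.0 / (2.4 × √(2/27)) = 2.0 / 0.653 = 3.06, giving power 0.807. At n = 26 power is 0.790. The smallest n reaching 80% is therefore 27, as stated.

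**2. Gaps at end of treatment.** PNS+PT: 0.875 × 8 = 7.0. PNS+shamPT: 5.0. PT+shamPNS: 0.34 × 8 = 2.72.

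- PNS+PT minus PT+shamPNS: 7.0 − 2.72 = 4.28
- PNS+PT minus PNS+shamPT: 7.0 − 5.0 = 2.0
- PNS+shamPT minus PT+shamPNS: 5.0 − 2.72 = 2.28

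**3. Can the sentence be right as written?** Two points more than PT+shamPNS would be 2.72 + 2 = 4.72 points, or 59% of 8. That is not 87.5%, and it falls below the 5.0 of PNS+shamPT, against the stated ordering. A different baseline does not help: 0.875b − 0.34b = 2 gives b = 2/0.535 = 3.74, below the entry minimum of 4 (Protocol 9.1). So the label is wrong, and the only arm that fits is PNS+shamPT.

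**4. Does the label reach the sample size?** The smallest 28-week gap is what matters. The wording for PT+shamPNS at the end of follow-up is unclear, so both readings are shown (SD 2.4, one-sided 0.05/3).

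| 28-week contrast | PT at 20% (1.6 points) | PT still at 34% (2.72 points) |
|---|---|---|
| PNS+PT vs PNS+shamPT | 2.0: 27 per group | 2.0: 27 per group |
| PNS+shamPT vs PT+shamPNS | 3.4: 11 per group | 2.28: 21 per group |
| PNS+PT vs PT+shamPNS | 5.4: 5 per group | 4.28: 7 per group |

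The smallest gap is 2.0 either way, so 27 per group covers all three contrasts. For PNS versus PT, power at 27 per group is about 99.8% on the first reading and about 90% on the second.

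**The case for a change.** The best case for acting is that this is a certain error in the design rationale and could be mended in a sentence or two. The SAP never says which pair sets the 80%. A reader who trusts the PNS+PT sentence would look for it in a comparison with PT, although the least-powered contrast is PNS+PT versus PNS+shamPT. A non-significant result there means less than a non-significant PNS versus PT result would, and the text does not help a reader see that.

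Part of this stands: the label is wrong and the binding pair is not named. The rest carries less weight.

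- The wrong label is in an end-of-treatment expectation. The sizing sentence concerns 28 weeks, speaks only of groups, and rests 2.0 on clinical importance.
- Its wording already makes 2.0 a lower bound on the gap and 27 a minimum, over three pairwise comparisons. It follows that larger gaps have more power.
- A power figure for each contrast would add reporting detail and settle no design question. For PNS versus PT it would also depend on how the 20% is read. Figure 7, which plots the trajectories, is not available here. Nor are the data-analysis and revised sample-size attachments listed in Protocol 10.4, so any silence can be claimed only for the SAP text.
- A null result will be read from its estimate and confidence interval, which do not depend on this sentence.

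**Conclusion.** The slip is real: the gap to the arm named is 4.28 points, and the 2 points belong to PNS+shamPT. It is clerical. The paragraph's own figures and ordering identify the intended arm without guesswork, and no number that the trial relies on was derived from the wrong label. The 2.0-point effect, 80% power, 27 per group and 96 participants are the same with either arm name, as are the conduct and the mixed-model analysis. No change to the plan is needed.

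This rests on a common baseline of 8 and on an equal split of alpha over three one-sided tests, which reproduces the stated 27. It does not depend on how the 28-week PT+shamPNS figure is read, since the smallest planned gap is 2.0 on both readings. Whether 32 per group allows adequately for 20% drop-out is a separate question that the label does not touch.

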bion® microstimulator (investigational): Due to the effectiveness of electrical stimulation but the difficulties associated with surface electrical stimulation, researchers have begun to investigate direct muscle and nerve stimulation. The bion® microstimulator used by Bioness, Inc. (Valencia, CA), is currently being investigated for the treatment of post-stroke shoulder pain and subluxation. Although the bion has technical advantages, including its small size and selfcontained electrode, it also suffers from considerable disadvantages. First, the device does not utilize a trial stage to evaluate whether a candidate is likely to experience pain relief from long term use prior to implantation. Second, implantation of the bion requires fluoroscopy and precise placement in close proximity to the deep axillary nerve trunk. Third, the device must be recharged daily using a large, stationary charging apparatus, to which the patient must be tethered during the recharging session. In addition, the bion's extraction requires open surgery. Finally, the bion requires precise placement due to its bipolar configuration, as the stimulus current density (and efficiency of nerve recruitment) drops off rapidly with distance from the target nerve. Even a small migration of the bion could significantly diminish its effectiveness. Data regarding the safe and effective use of the bion for post-stroke shoulder pain have not yet been published.

10.3 What are the outcome variables and how will they be analyzed? What are the statistical and analytical methods that will be used? Note this section can be copied from the NIH Grant Application or from the Statistical and Analytical Methods section of the industry trial protocol.

See attachments below.

Define outcomes and describe data analysis, please include a power calculation.

10.4 If the above requested information does not fit in the text box please attach a word document here:

If the requested information does not fit in the text box please attach a word document.

Name Description

Data Analysis (inc. Sample Size Calculation under Expectations and Analysis, Aim 1) | History
Outcomes Measures | History
Revised Sample Size Wilson PNS+PT R01 (2016 10 12) | History

View: 10-01 Risk/Benefits

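### The SAP names no rule for spending its combined one-sided alpha over three week-28 pain comparisons; stating one, preferably Holm step-down, is a cheap optional improvement on the equal split that the sizing suggests

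*SAP*

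**What the plan says.** The SAP's Expectations and Analysis text (Hypothesis 1) sets the planning difference and its visit: "The anticipated difference of at least 2.0 points between groups at 28-wks is the minimum clinically important difference in pain scores". The error rate, power and spread follow: "In order to detect this difference with 80% power, α =0.05 (combined), and anticipated SD of 2.4". The test is named next: "when using a one-sided, two-sample, equal-variance t-test of 3 pairwise comparisons", in the assumed order PNS+PT, then PNS+sham PT, then PT+sham PNS. This gives 27 per group. For loss to follow-up: "With the anticipated drop-out rate of 20%, this leads to a sample size of 32/group for a total of 96 participants".

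The analysis itself is a linear mixed effects model: "These mixed effects models yield estimates of the treatment, time and treatment by time while permitting us to control for potential confounders". For Aim 2 the SAP only refers back: "Continuous data will be analyzed using the approach described for hypotheses 1". Neither paragraph names a multiplicity procedure, writes out the three contrasts, or repeats the visit or the sidedness.

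Protocol 7.1 (Abstract) makes confirmation of PNS over PT the primary objective and the multimodal comparison the second objective.

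**The concern.** The word combined shows that the three tests share one error budget, but nothing says how. If the budget is a fixed equal split, each contrast is tested at one third of alpha even after the other two have been rejected. That is valid but gives up power.

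The loss falls mainly on PNS+PT versus PNS. Hypothesis 2 is an ordering, and this contrast has the smallest planned week-28 difference, so it decides whether the ordering can be claimed.

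The mixed-model paragraph adds a smaller gap. With seven post-baseline visits (Protocol 8.4, Study Summary), a treatment-by-time term alone does not identify the primary test. The sizing text makes the intention largely recoverable, so this is a matter of wording.

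**Working it through.** **1. Reproducing 27 per group.** SAP inputs: difference 2.0, SD 2.4, power 80%, one-sided, equal variances, three comparisons.

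Normal approximation at one-sided 0.05/3: n = 2 × (2.128 + 0.842)² × (2.4/2.0)² = 25.4, so 26. The exact t-test adds one. With n = 27 the noncentrality is 2.0 / (2.4 × √(2/27)) = 3.06 on 52 degrees of freedom, and power is 80.7%. With n = 26 it is 79.1%.

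| Per-test level | n per group for 80% (exact t) |
|---|---|
| one-sided 0.05 | 19 |
| two-sided 0.05 | 24 |
| one-sided 0.05/3 = 0.01667 (Bonferroni) | 27 (80.7%) |
| one-sided 0.01695 (Sidak) | 27 (80.9%) |
| two-sided 0.05/3 | 32 |

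The SAP's figure needs about 0.05/3 per test. The arithmetic cannot separate Bonferroni, Sidak and the first step of Holm.

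**2. Planned week-28 reductions.** From a baseline of 8, PNS+PT is 87.5% of 8 = 7 and PNS is 5. For PT the SAP says "a 34% reduction is anticipated by the end of treatment for PT+shamPNS group, increasing to a 20% decrease by the end of follow-up", and 20% of 8 = 1.6. The differences are 7 − 5 = 2.0 (PNS+PT vs PNS), 5 − 1.6 = 3.4 (PNS vs PT) and 7 − 1.6 = 5.4 (PNS+PT vs PT).

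**3. Completers.** 32 × 0.8 = 25.6, so 25 to 26 per group.

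**4. Equal split (0.05/3 each) against Holm (0.05/3, 0.05/2, 0.05).** Simulated pairwise t-tests with shared arms, SD 2.4. Reductions are listed as PNS+PT / PNS / PT. Power is for PNS+PT vs PNS at n = 25 / 26.

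| Reductions | Equal split | Holm |
|---|---|---|
| 7 / 5 / 1.6 (SAP percentages) | 77.1% / 79.1% | 89.5% / 90.7% |
| 2 / 0 / −1 | 77.2% / 79.2% | 85.7% / 87.3% |
| 2 / 0 / 0 | 77.3% / 79.0% | 81.0% / 82.6% |
| 2 / 0 / 1 | 77.3% / 79.2% | 77.8% / 79.7% |

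- All three contrasts together at 7/5/1.6, n = 26: 78.9% to 90.7%.
- Only one difference in the hypothesised direction (0/2/0, n = 27, PNS vs PT): 80.8% under both rules. By symmetry the same holds for PNS+PT vs PNS at 2/0/2.
- PNS vs PT at 7/5/1.6: 99.7% (n = 25) and 99.8% (n = 26) under the equal split, above 99.9% under Holm.

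**5. Error control.** Under the global null, any rejection occurs in about 4.5% of trials under both rules. With one true null and two large effects, Holm is at 5.0%, within simulation error of its exact limit. No simulated trial had a Bonferroni rejection that Holm missed.

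**6. Under the planned mixed model.** The documents give no within-subject correlation, so a range is assumed. Setting: 32 per arm, seven post-baseline visits, even monotone loss to 20%, visit SD 2.4, 60 degrees of freedom, reductions 7/5/1.6, PNS+PT vs PNS.

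| Model and assumed correlation | Equal split | Holm |
|---|---|---|
| No baseline covariate, compound symmetry, 0 to 0.7 | 79-83% | 90-93% |
| Baseline covariate, compound symmetry, 0.3 | 83.4% | 93.0% |
| Baseline covariate, compound symmetry, 0.5 | 90.5% | 96.6% |
| Baseline covariate, compound symmetry, 0.7 | 98.1% | 99.5% |
| Baseline covariate, AR(1), 0.3 to 0.7 | 79-80% | 90-91% |

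**The case against.** Four points stand against giving this much weight.

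- **The rule is inferred.** A reader might conclude that the SAP prescribes Bonferroni. It does not: Holm sized on its first step also gives 27. Protocol 10.4 lists separate attachments, among them "Data Analysis (inc. Sample Size Calculation under Expectations and Analysis, Aim 1" and a revised sample size file, and one of these may define what combined means.
- **Holm is not better in every case against every rule.** It dominates Bonferroni exactly. Against Sidak its first step is slightly stricter (0.01667 vs 0.01695). In 400,000 simulated trials at n = 26, Sidak rejected something that Holm missed in 0.13% (2/0/0) and 0.21% (2/0/1). This is negligible, but a claim that Holm never rejects less holds only against Bonferroni.
- **The large gain is a best case.** It needs the other two contrasts to be near certain. It also rests on one reading of a sentence that conflicts with itself: 87.5% of 8 is 7, but 2 points more than PT at end of treatment is 0.34 × 8 + 2 = 4.72, which is below the 5 planned for PNS alone. On that second reading neither rule has useful power for PNS+PT vs PNS.
- **The gain is on the second objective.** The primary-objective contrast gains almost nothing.

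A reader might also infer that the equal split leaves the trial short of 80% and that Holm repairs it. The completer figures of 77-79% invite this, but the planned analysis is a mixed model, under which the equal split may already reach 80% or more. The shortfall in completers comes from the dropout inflation (27/0.8 = 33.75 against the stated 32), which is a separate point, as is the conflict over the planned PNS+PT reduction.

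What survives is that the rule is unwritten, and that Holm is at least as good as Bonferroni at the same sample size and family-wise alpha.

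**Conclusion.** The point holds as a minor, optional improvement, not as an error in a stated rule. The sizing is consistent with a one-sided family-wise alpha of 0.05 shared over three week-28 contrasts, most naturally in equal parts, and the analysis text should say so.

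If the equal split is intended, Holm adds about 12 points of power for PNS+PT vs PNS in completer t-tests when the reductions are 7/5/1.6. It adds about 8 points at 2/0/−1, about 4 at 2/0/0, about 0.5 at 2/0/1, and nothing when only one difference favours the hypothesised order. These figures assume SD 2.4 and 25 to 26 completers per group. Mixed-model gains at 7/5/1.6 run from about 11 points down to about 1, depending on a correlation that the documents do not give.

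**What to change.** Add to the mixed-model paragraph: visit is categorical; the primary family is the three one-sided week-28 BPI SF-3 contrasts (PNS+PT vs PNS, PNS vs PT, PNS+PT vs PT); family-wise alpha is one-sided 0.05, tested by Holm at 0.05/3, 0.05/2 and 0.05; other visits and the responder analyses are supportive.

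If the team prefers the equal split for its simpler simultaneous intervals, writing that rule, the visit and the sidedness into the same paragraph closes the wording gap.

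The cost is SAP text only, with no extra patients or data, and less direct simultaneous intervals under a step-down rule. Timing matters. The protocol's CRU application gives an anticipated end date of 5/31/2021 and the SAP cover page is dated 11/5/2021, though the text may be older. The documents do not say whether treatment-level results had been seen. If they had, Holm should be labelled post hoc and the equal-split result shown beside it.

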## 8.1 Methods and Procedures II:

**8.4** \* Please specify in detail the methods and procedures that are involved in this research.

Study Summary: This is a multi-site, placebo controlled, double-blinded RCT to confirm the superiority of PNS over PT in reducing HSP, and to determine if multimodal treatment of HSP with PNS + PT is more efficacious than PNS or PT alone. The standard of care for treating shoulder pain is to try several options, most commonly including medications, injections and therapy. Candidates considering this study likely have tried some treatments but without lasting success. Ninety-six participants will be randomized to receive PNS + PT, PNS + sham-PT, or sham-PNS + PT. The PNS + PT group will receive active PNS therapy for 6 hours per day for 3 weeks along with 8 sessions of PT to improve biomechanics of the affected shoulder. The PNS+ sham-PT group will receive active PNS therapy and sham-PT, consisting of placebo ultrasound, application of inert gel, lower limb strengthening, and walking exercises. The sham-PNS + PT group will receive a percutaneous lead in a similar manner as the active therapy groups, but with sham-stimulation, along with 8 sessions of PT. Measures of pain, pain interference with ADLs, QoL, shoulder biomechanics (shoulder abduction torque, shoulder kinematics, and Fugl-Meyer score), and measures of central sensitization (pain thresholds, secondary hyperalgesia, and temporal summation) will be assessed at baseline and at weeks 4 (end of treatment), 8, 12, 16, 20, 24, and 28.

Baseline Variables and Randomization: Baseline data will be collected so that the balance of covariates across the three groups can be evaluated. Each participant will be characterized with respect to demographics, comorbidities, and medication use. Study outcome measures (see Outcomes Assessment) will be administered to establish baseline levels. Participants are assigned to treatment groups using an adaptive randomization algorithm [90-92] to minimize group imbalances on key patient characteristics: baseline pain (>6 or <=6) [93], duration of pain (>=18 months or <18 months) [15], age (>=55 years or <55 years) and study site. For each assignment, the algorithm calculates the balance of these variables across the groups and makes an assignment that would result in greater balance in the variables across groups.

Check all that apply.

Check all that apply.

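### 32 per group with 20% drop-out leaves 25.6, below the SAP's own minimum of 27; power on the sizing t-test is about 78%, not 80%

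*SAP*

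**What the plan says.** The sample size paragraph of the SAP (Expectations and Analysis, Hypothesis 1) sets the target as follows: "The anticipated difference of at least 2.0 points between groups at 28-wks is the minimum clinically important difference in pain scores". It continues: "In order to detect this difference with 80% power, α =0.05 (combined), and anticipated SD of 2.4, the minimum sample size is 27/group", using a one-sided, equal-variance, two-sample t-test for three pairwise comparisons. The drop-out step is one sentence, with no formula: "With the anticipated drop-out rate of 20%, this leads to a sample size of 32/group for a total of 96 participants".

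The protocol (8.4, Study Summary) uses the same total: "Ninety-six participants will be randomized to receive PNS + PT, PNS + sham-PT, or sham-PNS + PT". Outcomes "will be assessed at baseline and at weeks 4 (end of treatment), 8, 12, 16, 20, 24, and 28".

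For the analysis, the SAP plans a different method from the sizing t-test: "Each measure will be modeled using a linear mixed effects approach which is well-suited for handling correlated repeated measurements".

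The same SAP paragraph gives the anticipated effect of combined treatment: "We anticipate an 87.5% reduction, or 2-points more than PT +shamPNS, by end of treatment for the PNS+PT group".

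**The concern.** The SAP calls 27 per group a minimum and expects to lose one participant in five. The number randomised should then be one that still leaves 27 after that loss, and 32 is not. As written, the stated power, drop-out rate and sample size cannot all be true on the method the SAP uses.

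At stake is how accurate the 80% claim is for the smallest planned contrast, whether adding PT to PNS improves on PNS alone (part of Aim 2).

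A labelling slip in the same paragraph makes it harder to see which contrast that is. The 87.5% sentence attaches the 2-point advantage to PT+shamPNS, whereas the SAP's own figures attach it to PNS+shamPT.

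**Working it through.** **Inputs, all from the SAP sample size paragraph**

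- Difference 2.0 points, SD 2.4, target power 80%.
- One-sided two-sample t-test, three pairwise comparisons, combined alpha 0.05. I read this as 0.05/3 = 0.0167 per comparison. That split is an assumption, since the SAP names no procedure; a Šidák split gives the same n.
- Minimum 27 per group, drop-out 20%, 32 per group, 96 in total.

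**Step 1: reproduce the 27.** With n per group, the noncentrality is 2.0 / (2.4 × √(2/n)) on 2n − 2 degrees of freedom. Power from the noncentral t distribution:

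| n per group | Power |
|---|---|
| 25 | 77.3% |
| 25.6 | 78.4% |
| 26 | 79.05% |
| 27 | 80.7% |

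The smallest n that reaches 80% is 27, exactly as stated. Other readings do not give 27: one-sided 0.05 without adjustment gives 19, two-sided 0.05 gives 24, and two-sided 0.05/3 gives 32.

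**Step 2: the drop-out step.**

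- Completers from 32 per group: 32 × (1 − 0.20) = 25.6, below 27.
- Number needed to keep 27: 27 / (1 − 0.20) = 33.75, so 34 per group and 3 × 34 = 102 in total.
- Drop-out that 32 per group can absorb: 1 − 27/32 = 15.6%.
- Possible origin of 32: 27 × 1.2 = 32.4, rounded down. This is an inference, because the SAP shows no formula.

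**Step 3: size of the shortfall.** Power at 25.6 per group is 78.4%, which is 80 − 78.4 = 1.6 points short of the target.

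**Step 4: which contrasts are affected.** The SAP assumes a baseline of 8. Anticipated reductions at week 28 are 0.875 × 8 = 7.0 for PNS+PT, 5.0 for PNS+shamPT, and 0.20 × 8 = 1.6 for PT+shamPNS.

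| Contrast at week 28 | Planned difference | Power at 25.6 per group |
|---|---|---|
| PNS+PT vs PNS+shamPT | 7.0 − 5.0 = 2.0 | 78.4% |
| PNS+shamPT vs PT+shamPNS | 5.0 − 1.6 = 3.4 | 99.8% |
| PNS+PT vs PT+shamPNS | 7.0 − 1.6 = 5.4 | over 99.9% |

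**Step 5: what the mixed model might recover.** The documents give neither the correlation between visits nor the timing of drop-out, so this is a sensitivity range on assumed values. Data are taken as missing at random. A share f of drop-outs (50% to 100%) has an earlier post-baseline visit, whose correlation ρ with week 28 is 0.3 to 0.7. With 32 − 25.6 = 6.4 drop-outs per group, the large-sample effective number is

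1 / [ρ² / (25.6 + 6.4f) + (1 − ρ²) / 25.6].

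| f | ρ | Effective n | Power |
|---|---|---|---|
| 0.5 | 0.3 | 25.86 | 78.8% |
| 0.5 | 0.5 | 26.33 | 79.6% |
| 0.5 | 0.7 | 27.07 | 80.8% |
| 1 | 0.3 | 26.07 | 79.2% |
| 1 | 0.5 | 26.95 | 80.6% |
| 1 | 0.7 | 28.38 | 82.8% |

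**Step 6: the comparator label.** The anticipated end-of-treatment reduction for PT+shamPNS is 0.34 × 8 = 2.72. A 7.0-point reduction is therefore 7.0 − 2.72 = 4.28 points more than PT+shamPNS and 7.0 − 5.0 = 2.0 points more than PNS+shamPT. The sizing used 2.0, so the label did not enter the calculation.

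**The case against.** The arithmetic is hard to dispute; the case on the other side is about materiality and precision.

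- **The gap is within planning error.** A shortfall of 1.6 power points, or two participants per group, is smaller than the uncertainty in an assumed SD of 2.4 and drop-out of 20%. If drop-out is 15.6% or less, the shortfall disappears. This stands, and it is why the point is minor.
- **The planned analysis is a mixed model.** Drop-outs with earlier visits still contribute, and the range in step 5 straddles 80%. This also stands: 78% is the power of the sizing t-test only. It does not rescue the SAP sentence, though. The 80% claim rests on that t-test, and by inflating for drop-out the SAP itself treats drop-outs as lost.
- **A normal approximation gives 80.3% at 25.6 per group.** It does, but it also gives a minimum of 26, not 27, and the SAP names a t-test. Even 26 exceeds 25.6.
- **The reassurance on the other contrasts depends on reading one odd sentence.** The SAP gives a 34% reduction for PT+shamPNS at end of treatment, then describes a move to 20% by the end of follow-up as an increase. I read this literally as a 20% reduction at week 28; Figure 7, which might settle it, is not available here. If the 34% persisted instead, PNS+shamPT vs PT+shamPNS would be 5.0 − 2.72 = 2.28 points, with 88.3% power at 25.6 per group. That is still above 80%, but the 99.8% is conditional on the reading.
- **A separate sample size attachment exists.** Protocol 10.4 lists one, but no text under that name is among the documents. It might explain the 32; it could not make 32 × 0.8 equal 27.
- **Timing.** The SAP is dated after the anticipated study end date in the protocol. If that date held, the correction serves the record only.

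**Conclusion.** The concern holds. A minimum of 27, a 20% drop-out and 32 per group are inconsistent on the SAP's own method. That method gives 78.4% power for a 2.0-point difference at 25.6 per group.

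The conclusion rests on the 0.05/3 split, which is the reading that returns the SAP's 27. Confining the shortfall to PNS+PT vs PNS+shamPT rests on the SAP's anticipated means; the PNS versus PT comparison of Aim 1 stays above 80% under either reading of the PT trajectory. The power of the final mixed-model analysis cannot be fixed from the documents and may lie slightly either side of 80%. Severity is minor.

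**What to change.** Keep 96 participants and restate the power. Suggested wording for the SAP:

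> With 32 per group and 20% drop-out, about 25 to 26 per group are expected to complete. This gives about 78% power for a 2.0-point difference on the two-sample t-test used for sizing, and at least 80% if drop-out does not exceed 15.6%. The mixed model may recover some power from partial data.

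State how the combined alpha is divided and add the three-contrast table from step 4, marked as conditional on the anticipated means. Clarify the sentence on the PT+shamPNS trajectory so that the 1.6-point reduction at week 28 is explicit. In the 87.5% sentence, change the comparator from PT+shamPNS to PNS+shamPT.

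The cost is SAP wording only. The number randomised, the conduct and the analysis do not change; the stated power for one contrast falls by about 2 points.
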